This document cannot be used to support any marketing authorization application and any extensions or variations thereof.

4. LIST OF ABBREVIATIONS

AE	Adverse event
AED(s)	Antiepileptic Drug(s)
ALT(ALAT/SGPT)	Alanine Aminotransferase
AST (ASAT/SGOT)	Aspartate Aminotransferase
b.i.d.	Twice daily
BRV	brivaracetam
CNS	Central Nervous System
CPM	Clinical Project Manager
Cr Cl	Creatinine Clearance
CRF	Case Report Form
CRO	Clinical Research Organization
C-SSRS	Columbia Suicide Severity Rating Scale
CTM	Clinical Trial Manager
CTS	Clinical Trials Supplies
CV	Curriculum Vitae
CYP	Cytochrome P450
DRC	Daily Record Card
ECG	Electrocardiogram
EDV	Early Discontinuation Visit
EEG	Electroencephalogram
EQ-5D	EuroQoL-5 Dimensions
GCP	Good Clinical Practice
GMP	Good Manufacturing Practice
GP	General Practitioner
HADS	Hospital Anxiety and Depression Scale
HDL	High Density Lipoprotein
HIPAA	Health Insurance Portability and Accountability Act
ICH	International Conference on Harmonization
IEC	Independent Ethics Committee
ILAE	International League Against Epilepsy
IRB	Institutional Review Board
IVRS	Interactive Voice Response System
LTFU	Long-term Follow-up
MCH	Mean Corpuscular Haemoglobin
MCHC	Mean Corpuscular Haemoglobin Concentration
MCV	Mean Corpuscular Volume
MedDRA	Medical Dictionary for Regulatory Activities
MRI	Magnetic Resonance Imaging
PBO	Placebo
PK	Pharmacokinetic(s)

This document cannot be used to support any regulatory application and any extensions or variations thereof.

POS	Partial onset seizure(s)
PRO	Patient Reported Outcome
QOLIE-31-P	Patient Weighted Quality of Life in Epilepsy Questionnaire
RBC	Red Blood Cell
SAE	Serious adverse event
SAP	Statistical Analysis Plan
SUSAR	Suspected Unexpected Serious Adverse Reaction
SV2A	Synaptic vesicle protein 2A
TEAE	Treatment-emergent adverse event
TMF	Trial Master File
V	Visit
WBC	White Blood Cell

REDACTED COPY
This document cannot be used to support any marketing authorization application and any extensions or variations thereof.

5. PROTOCOL SUMMARY

TITLE OF THE STUDY

An open-label, multinational, multicenter, follow-up study to evaluate the long-term safety and efficacy of brivaracetam used at a flexible dose up to a maximum of 200mg/day in subjects aged 16 years or older suffering from epilepsy.

STUDY TYPE/PHASE

Phase III

STUDY OBJECTIVES

Primary Objective

To evaluate the long-term safety and tolerability of brivaracetam (BRV) at individualized doses with a maximum of 200mg/day in subjects suffering from epilepsy.

Secondary Objective

To evaluate the maintenance of efficacy over time of BRV.

Exploratory Objectives

- To explore impact on health-related quality of life, anxiety and depression.
- To obtain a description of patient's self-reported health status.
- To collect data on medical resources used and on indirect cost parameters.

STUDY VARIABLES

Primary Safety Variables

- Occurrence of a treatment-emergent adverse event (TEAE)
- Withdrawal due to AE
- Occurrence of a serious adverse event (SAE)

Other Safety Variables

- Laboratory tests (blood chemistry, hematology, and urinalysis)
- Vital signs (systolic blood pressure [SBP], diastolic blood pressure [DBP], pulse rate) and body weight
- Electrocardiogram (ECG)
- Physical and neurological examination

- Change in Hospital Anxiety and Depression Scale (HADS) scores from the Baseline of the previous study to each assessment for the first 2 years and to the last Evaluation Period assessment during the first 2 years

Secondary Efficacy Variables

- Percentage of subjects on continuous BRV monotherapy for at least 3 months, at least 6 months, and at least 12 months of the Evaluation Period

Other Efficacy Variables

- Partial onset seizure (POS) (type I) frequency per 28 days during the Evaluation Period
- Percent reduction in POS (type I) frequency per 28 days from Baseline of the previous study to the Evaluation Period
- Percentage of subjects continuously seizure-free for all seizure types (I+II+III) for at least 6 months and at least 12 months during the Evaluation Period
- Change in Patient Weighted Quality of Life in Epilepsy Questionnaire (QOLIE-31-P) scores from Baseline of the previous study to each assessment for the first 2 years and to the last Evaluation Period assessment during the first 2 years
- EuroQoL-5 Dimensions (EQ-5D) questionnaire response for each assessment for the first 2 years for the Evaluation Period and for the last assessment during the first 2 years of the Evaluation Period

Pharmacoeconomic Variables

- Direct costs (healthcare provider consultations not foreseen by the protocol, concurrent medical procedures, concomitant medications, hospitalizations, and emergency room [ER] visits) during the first 2 years of the Evaluation Period
- Indirect costs (workdays or schooldays lost by the subject and days subject received help from a caregiver) during the first 2 years of the Evaluation Period
- Socio-professional data for each assessment for the first 2 years and for the last assessment during the first 2 years of the Evaluation Period

Pharmacokinetic Variables

- Brivaracetam (parent compound only) plasma levels
- Concomitant antiepileptic drugs (AEDs) (and/or relevant metabolites) plasma levels

STUDY DESIGN

This is a Phase III, long-term follow-up (LTFU), multinational, multicenter, non-comparative, open-label and single arm study.

The visits will be scheduled as follows:

- First year:
 - First 3 months: 1 visit/month: Full Evaluation Visit (FEV) alternating with Minimal Evaluation Visit (MEV).
 - Next 9 months: 1 visit/3 months: FEV alternating with MEV.
- Second and subsequent years:
 - 1 visit/3 months: FEV alternating with MEV.
 - The Yearly Evaluation Visit (YEV) will be performed in replacement of the first FEV of each year.

PLANNED STUDY PERIOD

This study will run throughout the duration of the clinical development period of BRV, and will continue until a marketing authorization is granted by any Health Authority in an indication for the adjunctive treatment in adults with refractory POS, whether or not secondarily generalized, until the Sponsor decides to close the study, until subjects transition to another BRV study, until a managed access program, named patient program, compassionate use program, or similar type of access program is established as allowed per country-specific requirements in addition to legal and regulatory guidelines, or until BRV development is stopped by the Sponsor.

PLANNED NUMBER OF SUBJECTS AND SITES:

It was estimated that approximately 300-600 subjects were to enter the study. However, the number of subjects entered will be reduced due to the premature discontinuation of N01276 and N01306.

This study will include as many sites as required (initially, 120-180 sites are foreseen).

REGIONS AND COUNTRIES

The study is planned to be performed worldwide.

MAIN INCLUSION AND EXCLUSION CRITERIA

Before any study procedures are initiated for any subject in this study, an Independent Ethics Committee (IEC)/Institutional Review Board (IRB) approved written informed consent form will be properly executed and documented.

Subject Inclusion Criteria:

- An IEC/IRB approved written informed consent signed and dated by the subject or by parent(s) or legally acceptable representative. The consent form or a specific assent form, where required, will be signed and dated by minors.

- Male/female subjects from 16 years or older. Subjects under 18 years may only be included where legally permitted and ethically accepted. In [REDACTED] all subjects must be older than 18 years.
- Subjects with epilepsy who participated in previous BRV studies which allow access to the present study.
- Subjects from whom the Investigator believes a reasonable potential benefit from the long-term administration of BRV may be expected.
- Female subjects without childbearing potential (premenarcheal; 2 years postmenopausal, bilateral oophorectomy or ovariectomy, bilateral salpingectomy, complete hysterectomy, congenital sterility) are eligible. Female subjects with childbearing potential are eligible if they use a medically accepted contraceptive method for the duration of the study (Intra Uterine Device, diaphragm with spermicide, male or female condom with spermicide; oral hormonal contraceptive, non-oral hormonal contraceptive medication, bilateral tubal ligation, bilateral tubal implant, monogamous relationship with vasectomized partner). Oral or depot contraceptive treatment with at least 30µg [or 50µg if associated with other antiepileptic drugs known as inducers] ethinylestradiol per intake must be used in conjunction with a barrier method. The subject must understand the consequences and potential risks of inadequately protected sexual activity, be educated about and understand the proper use of contraceptive methods, and undertake to inform the Investigator of any potential change in status. Sexual inactivity might be accepted on a case-by-case basis.
- Subject/legally acceptable representative considered as reliable and capable of adhering to the protocol (e.g. able to understand and complete diaries and questionnaires), visit schedule or medication intake according to the judgment of the Investigator.

Subject Exclusion Criteria:

- Severe medical, neurological and psychiatric disorders, including current suicidal ideation or behaviour, or laboratory values which may have an impact on the safety of the subject, as determined by the Investigator.
- Poor compliance with the visit schedule or medication intake in the previous BRV study.
- Participation in any clinical study of another investigation drug or device during the study.
- Pregnant or lactating woman.

INVESTIGATIONAL PRODUCT

Oral tablets of 10mg and 25mg BRV, packaged in bottles containing 200 oral tablets.

Subjects will begin at a recommended dose of BRV 100mg/day. The daily dose should be divided into 2 equal intakes (morning and evening), taken with or without food. The first intake will be in the evening of the day of the dispensation of the study medication.

Subjects will continue BRV treatment at a dose up to a maximum of 200mg/day in twice daily (b.i.d.) administration. Up- and down-titration steps should be performed in steps of

maximum 50mg/day on a weekly basis. Full down-titration should include a 1-week step on 20mg/day.

The doses administered in this study must comply with doses that can be administered with either BRV 10mg tablets, 25mg tablets, or a combination of these 2 strengths in a total daily dose that can be administered in 2 equal doses. Daily dose prescriptions that do not respect these limitations should not be administered.

Each subject will be informed on how to take the drug and that there might be an excess of drug dispensed at each visit.

STATISTICAL METHODS

Population for Analysis

The Safety Population will consist of all subjects who took at least 1 dose of study medication.

The Efficacy Population will consist of all subjects who took at least 1 dose of study medication and have at least 1 seizure diary day during the Evaluation Period.

Safety Variables Analyses

All safety analyses will be summarized descriptively. Changes from Baseline will be calculated from the Baseline of the preceding study.

Efficacy Variables Analyses

No hypothesis testing will be performed.

All efficacy analyses will be summarized descriptively. The Baseline of an efficacy variable will be the Baseline from the initial study.

Sample Size Calculation

For this open-label, LTFU study, no sample size calculation has been performed. The sample size will depend upon recruitment into and completion of preceding studies; approximately 300 - 600 subjects were expected.

5.1 Study Schedule of Assessments

Table 5:1 Study Flowchart

	Entry Visit (EV)	Full Evaluation Visit (FEV)	Minimal Evaluation Visit (MEV)	Yearly Evaluation Visit (YEV)	Additional Visit (AV)	Early Discontinuation Visit (EDV) ^(f)	Down-Titration Phone Call (DTP) ^(a)	Final Visit (FV)	Reference to Section
ASSESSMENTS									
Written Informed Consent	X								11.1.1
Clinical Study Subject Card Dispensing	X								11.1.2
Verification Inclusion/ Exclusion Criteria	X								11.1.3
Demographic Data	X								11.1.4
Childbearing Potential	X								11.1.5
Medical and Procedures History	X ^(b)								11.1.6
Epilepsy History	X ^(b)								11.1.7
AED History	X ^(b)								11.1.8
Vital Signs	X ^(c)	X	X	X	X	X		X	11.1.9
Weight and Height ^(d)	X ^(c)	X		X		X		X	11.1.10
Physical Examination	X ^(c)	X		X		X		X	11.1.11
Neurological Examination	X ^(c)	X		X		X		X	11.1.12
ECG ^(e)	X ^(c)			X		X		X	11.1.13
Daily Record Card Dispensed	X ^(c)	X	X	X		X			11.1.14
Daily Record Card Retrieval		X	X	X		X		X	11.1.14
Seizure Counts	X	X	X	X		X		X	11.1.14
Recording of Seizures	X ^(c)	X	X	X		X		X	11.1.14
QOLIE-31-P ^(f)		X		X		X			11.1.20.1
HADS ^(f)		X		X		X			11.1.20.2
EQ-5D ^(f)		X		X		X			11.1.20.3

Table 5:1 Study Flowchart

	Entry Visit (EV)	Full Evaluation Visit (FEV)	Minimal Evaluation Visit (MEV)	Yearly Evaluation Visit (YEV)	Additional Visit (AV)	Early Discontinuation Visit (EDV) ^(d)	Down-Titration Phone Call (DTP) ^(a)	Final Visit (FV)	Reference to Section
ASSESSMENTS									
Workdays and schooldays lost / Days with caregiver's help ^(k)		X	X	X	X	X		X	
Hospital stay ^(k)		X	X	X	X	X		X	11.1.21
Healthcare Provider Consultations not foreseen by the protocol ^(k)		X	X	X	X	X		X	11.1.22
Socio-professional data ^(g)				X		X		X	11.1.23
Laboratory Assessments ^(h)	X ^(c)	X		X		X		X	11.1.15
Recording of Adverse Events	X	X	X	X	X	X	X	X	11.1.16
C-SSRS ^(j)		X	X	X	X	X		X	11.1.17
Medical Procedures	X	X	X	X	X	X		X	11.1.6
Concomitant AED	X	X	X	X	X	X		X	11.1.19
Concomitant Non-AED	X	X	X	X	X	X		X	11.1.19
Drug Dispensing	X	X	X	X		X			
Drug Return/Accountability		X	X	X		X		X	
End of Study Status ⁽ⁱ⁾								X	11.1.24

AED=antiepileptic drug; AV=Additional Visit; BRV=brivaracetam; CRF=Case Report Form; C-SSRS=Columbia Suicide Severity Rating Scale; DTP=Down-Titration Phone Call; ECG=electrocardiogram; EDV=Early Discontinuation Visit; EQ-5D=EuroQoL-5 Dimensions; EV=Entry Visit; FEV=Full Evaluation Visit; FV=Final Visit; HADS=Hospital Anxiety and Depression Scale; IEC=Independent Ethics Committee; IRB=Institutional Review Board; MEV=Minimal Evaluation Visit; QOLIE-31-P=Patient Weighted Quality of Life in Epilepsy Questionnaire; YEV=Yearly Evaluation Visit

- (a) Down-Titration Phone Call at the end of the Down-Titration Period is mandatory in case the subjects discontinue from more than 20mg/day BRV.
- (b) The following data will be obtained from the database of the Baseline Visit of the previous study and should not be recorded into the CRF: General Medical and Procedure History, AED History, and Epilepsy History.
- (c) The following data will be obtained from the database of the final visit of the previous study and should not be recorded in the CRF: Vital Signs, Weight, Physical Examination, Neurological Examination, ECG, Recording of seizures, Laboratory Assessment including Safety (blood chemistry, hematology, and urinalysis), concomitant AED plasma levels and BRV plasma levels.
- (d) Height will be recorded at Visit 1. Height will also be measured at each YEV and the FV for those subjects who are still potentially growing.

Table 5:1 Study Flowchart

	Entry Visit (EV)	Full Evaluation Visit (FEV)	Minimal Evaluation Visit (MEV)	Yearly Evaluation Visit (YEV)	Additional Visit (AV)	Early Discontinuation Visit (EDV) ^(l)	Down-Titration Phone Call (DTP) ^(a)	Final Visit (FV)	Reference to Section
ASSESSMENTS									

- ^(e) At FV, ECG is mandatory except if FV follows an EDV-where ECG results were normal.
- ^(f) QOLIE-31-P, EQ-5D, and HADS are to be completed at the beginning of the visit by all subjects who are not mentally impaired during the first 2 years.
- ^(g) Socio-professional data (to be collected during the first 2 years) will not be collected in [REDACTED]
- ^(h) Laboratory assessment includes blood chemistry, hematology, and urinalysis; where applicable (women of childbearing potential), a serum pregnancy test will be done. Laboratory is mandatory at FV except if FV follows an EDV where laboratory results were normal. Concomitant AED plasma levels and BRV plasma levels up to approval of Protocol Amendment 2.
- ⁽ⁱ⁾ End of study status will be completed at the FV for subjects having performed an EDV (discontinued subjects) and for subjects leaving the study at the end of the program (completed subjects).
- ^(j) The C-SSRS assessment will be implemented by site per IRB/IEC approval upon completion of required training. As of the time of Protocol Amendment 2, all subjects had completed their EV. Thus, the C-SSRS was not assessed for any subjects at their EV.
- ^(k) Procedures only performed during the first 2 years of subject participation in the study or EDV/FV in case the subject discontinues participation within the first 2 years.
- ^(l) For subjects that may transition to another BRV study or a managed access program or similar type of program, the EDV will need to be completed, however down-titration and FV may not be applicable.

This document cannot be used to support any marketing applications and all dimensions or variations thereof.

5.2 Schematic Diagram

- First year:
 - First 3 months: 1 visit/month: FEV alternating with MEV
 - Next 9 months: 1 visit/3 months: FEV alternating with MEV
- Second and subsequent years:
 - 1 visit/3months: FEV alternating with MEV
 - The YEV will be performed in replacement of the first FEV of each year.

Table 5:2 Visit Schematic Diagram

1st, 2nd and subsequent years follow-up		
Month	Visit	Type of Visit
M0	V1	Entry Visit (EV)
M1	V2	MEV
M2	V3	FEV
M3	V4	MEV
M4		
M5		
M6	V5	FEV
M7		
M8		
M9	V6	MEV
M10		
M11		
M12	V7	YEV
M15	V8	MEV
M18	V9	FEV
M21	V10	MEV
M24	V11	YEV
M...	V...	...

In case the subject will not continue with the study drug, the Investigator will first plan an Early Discontinuation Visit (EDV) followed by the progressive down-titration of the study drug. During the down-titration period, the dose may be decreased in steps of a maximum of 50mg/day on a weekly basis. A last down-titration step at 20mg/day for 1 week will be included prior to the drug free period.

At the end of the down-titration period, a phone call will be given to subjects having down-titrated from doses higher than 20mg/day. The down-titration period will be followed by a period free of study drug of a minimum of 2 weeks and a maximum of 4 weeks and subsequently, the Final Visit (FV) will occur.

When the time point is reached at which the study will be terminated by the Sponsor (as defined in Section 8.4), subjects will discontinue the study drug, following the Investigator's instructions for down-titration if necessary.

This document cannot be used to support any marketing authorization application and any extensions or variations thereof.

REDACTED COPY

6. BACKGROUND INFORMATION

6.1 Background and epidemiology of targeted disease

Epilepsy is 1 of the most common and challenging neurological disorders. It has been estimated that over 50 million people are affected worldwide (Engel and Pedley, 1998; Hauser et al, 1993; Loiseau et al, 1990; Sander and Shorvon, 1996). The prevalence of epilepsy is around 1%. The annual incidence in developed countries is around 50 to 70 cases per 100,000. In developing countries, the figure is higher due to more limited obstetric services and the greater likelihood of cerebral infection and trauma. The incidence varies greatly with age, with high rates occurring in childhood, falling to low levels in early adult life, but with a second peak in those aged over 65 years. In many people, particularly children, the condition may remit, although a significant proportion will have epilepsy lifelong. The disease duration is often determined by the underlying cause. Sudden unexpected death, a complication of great concern, occurs in 1 to 5 per 1000 patient years, particularly if the seizure disorder remains uncontrolled. The treatment for epilepsy remains difficult, and there is ongoing medical need for new AEDs. For considerable proportions of patients, seizure freedom can still not be reached with currently available AEDs (Nasreddine et al, 2010; Kwan and Brodie, 2001).

Diagnosis of epilepsy is based on the recurrence of seizures. Seizures may be caused by an underlying brain disorder or lesion or due to genetic conditions. Characterization of the epileptic syndrome has profound implications for treatment and prognosis. The major dichotomy for the diagnosis of epilepsy is the differentiation between focal epilepsies (i.e., related to a focal brain dysfunction), which are the most frequent and account for approximately 60 to 70% of all cases, and generalized epilepsy syndromes, which represent approximately 25 to 30% of all epilepsy syndromes. In about 10% of cases, other specific syndromes are classified or the classification remains uncertain.

The classification of epileptic syndromes and seizure types is – and always was – a matter of ongoing debate. First published in 1960 and last updated officially in 1981 for seizures and 1989 for epilepsies (Commission on Classification and Terminology of the International League Against Epilepsy ([ILAE], 1981 and 1989), these ILAE classifications were based on concepts that, for the most part, predate modern technologies and concepts (Engel, 2006; ILAE [<http://www.ilae-epilepsy.org>]). The availability of these modern techniques, like long-term video electroencephalograms (EEGs) and high-resolution magnetic resonance imaging (MRI), providing much more precise knowledge in regard to seizure type classifications and epileptic syndromes, led some epilepsy groups and scientists towards introducing competing classification systems (like the Cleveland Clinic Epilepsy Classification) and even debating how useful the currently used ILAE classification system is at all (Lüders et al, 2006).

This ongoing debate regarding the classification systems for epilepsies and seizures is also reflected within the latest Report of the Commission on Classification and Terminology (Classification Task Force) which proposes a thoroughly revised terminology and concept for the diagnosis of epilepsy syndromes and also to some extent seizure types (Berg et al, 2010).

Despite this ongoing debate, for the purpose of this study, the seizure type classification will follow the 1981 ILAE classification of epileptic seizures, which speaks of partial seizures, classified as simple partial seizures (no alteration of consciousness), complex partial seizures (with alteration of consciousness), and secondarily generalized seizures, and on the other hand defines generalized seizure types, referred to as absence seizures (typical and atypical), myoclonic seizures, clonic seizures, tonic seizures, tonic-clonic seizures, and atonic seizures. Apart from myoclonic seizures, consciousness is almost invariably impaired from the onset of the seizure (Commission on Classification and Terminology of the ILAE, 1981).

Likewise, the classification of epilepsy syndromes will be used according to the 1989 ILAE-publication (Commission on Classification and Terminology of the ILAE, 1989).

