## **2.4 Determination of Sample Size**

No sample size calculation was done. Sample size was dependent upon recruitment into and completion of preceding studies. At the time of development of this SAP, the enrollment into this study has been completed and a total of 108 subjects have been enrolled into N01315.

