### 3.2.4 Study periods

The study is divided into 3 periods: Evaluation Period, Down-Titration Period, and Post-Treatment Period. A subject is classified as “discontinued” if the subject has a termination case report form (CRF) or has an early discontinuation visit (EDV). A subject is classified as “completed” if this subject completes the full extent of the study as defined in the protocol at database lock.

A “discontinued” subject can be potentially slotted into the 3 periods of the study. The following algorithms will be used to slot the subject appropriately into the Evaluation Period, Down-Titration Period, and Post-Treatment Period.

- For Evaluation Period, the start date is the date of first dose of BRV, and the following algorithm is used to determine the end date:
  - If the subject enters the Down-Titration Period, then the date of EDV is the end date;
  - If the subject does not enter the Down-Titration Period but meets 1 of the following criteria, the Evaluation Period ends on date of last dose of BRV:
    - Without an EDV but having a termination CRF,
    - With an EDV and having a termination CRF,
    - With an EDV and the date of EDV prior to the database lock date and having no termination CRF.
- A subject is considered entering Down-Titration Period only if the subject has an EDV and at least 1 dose of study drug after the date of EDV, the start date of Down-Titration Period is set as 1 day after the date of EDV, and the Down-Titration Period ends on date of last dose of BRV. A subject without an EDV but having a termination CRF or with an EDV but without any dosing of study drug after the EDV will not have the Down-Titration Period, and no artificial Down-Titration Period will be created for analysis.
- A subject is considered entering the Post-Treatment Period if the subject has at least 1 contact (scheduled visit, unscheduled visit, or telephone contact) after the date of last dose of BRV. The Post-Treatment Period starts 1 day after date of last dose of BRV irrespective of entering the Down-Titration Period, and there is no end date.

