### 3.2.7 Exposure duration and exposure duration cohorts

At the final analysis, the overall duration of exposure (or On Treatment Period) will be calculated as the date of last dose of BRV minus the date of first dose of BRV plus 1 day.

Each subject will be classified into one or more of the following exposure duration cohorts based on the duration of BRV exposure as calculated above:

|              |           |
|--------------|-----------|
| All subjects | ≥1 day    |
| ≥3 months    | ≥90 days  |
| ≥6 months    | ≥180 days |
| ≥12 months   | ≥360 days |

This categorization will continue in 6-month increments past 12 months up to a time point that will be determined based on cumulative exposure at the time of the database lock.

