## 11.1 Extent of Exposure

### 11.1.1 Number of subjects exposed and subject-years of exposure

A daily dose will be calculated for each study day from the day of first dose of BRV to the day of last dose of BRV for the purposes of calculating modal dose. Daily dose will be calculated as the sum of the AM and PM dose for each day.

Modal daily doses will be calculated across all study days on or after the day of first dose of BRV and up to and including the day of last dose of BRV. Modal daily dose is the most frequently taken daily dose during this period. In the event of a tie, the modal dose will be set to the lower of the tied doses. Modal daily dose will be categorized as follows:

| Category  | Definition               |
|-----------|--------------------------|
| 5 mg/day  | <20mg/day                |
| 20mg/day  | ≥20mg/day to <50mg/day   |
| 50mg/day  | ≥50mg/day to <100mg/day  |
| 100mg/day | ≥100mg/day to <150mg/day |
| 150mg/day | ≥150mg/day to <200mg/day |
| 200mg/day | ≥200mg/day               |

Subject years of exposure will be calculated by summing the exposure duration in days for all subjects being summarized, and dividing the resulting value by 365.25.

Subject years of exposure will be presented overall and by modal dose for the Safety Analysis Set. The subject years of exposure presented by modal dose will be the total subject years of exposure of subjects with that modal dose.

The number and percentage of subjects exposed to BRV will be summarized overall and by modal dose category. The number and percentage of subjects in each Exposure Duration Cohort (≥3 months, ≥6 months, ≥12 months, and so forth) will be summarized.

The number and percentage of subjects within each modal dose category will be summarized for each Exposure Duration Cohorts; percentages will be relative to the total number of subjects in each Exposure Duration Cohort.

In addition to the overall summaries of the above, the above will also be summarized by subgroup for region.

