### 11.2.2 General summaries of TEAEs

Pre-treatment AEs will be provided in a subject data listing; no summaries of pre treatment AEs are planned.

An overall summary of AEs will provide the overall number of TEAEs and the numbers and percentages of subjects with at least 1 TEAE, with a TEAE that led to permanent discontinuation of study drug, with a drug-related TEAE, with a severe TEAE, with a treatment-emergent SAE, and with a drug-related treatment-emergent SAE. The number and percentage of subjects who died will also be summarized. This summary will be provided for all subjects in the Safety Analysis Set and also by subgroup for geographic region.

The following summaries of TEAEs will be provided by MedDRA SOC and PT. All summaries are for the combined Evaluation, Down-Titration, and Post-Treatment Periods unless otherwise indicated.

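### Deaths are to be reported only as a count and percentage, with no rate per subject-year and no at-risk window, although follow-up is open-ended and unequal

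*Protocol*

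**What the plan says.** **Deaths.** SAP 11.2.2 states: "The number and percentage of subjects who died will also be summarized". This is done for the Safety Analysis Set and by geographic region. No rate per subject-year is planned for deaths or for any other adverse event, and the death line names no period. The next paragraph of the same section, which governs the tables by system organ class and preferred term, says: "All summaries are for the combined Evaluation, Down-Titration, and Post-Treatment Periods unless otherwise indicated".

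**Exposure.** SAP 11.1.1 states: "Subject years of exposure will be calculated by summing the exposure duration in days for all subjects being summarized", divided by 365.25. It adds: "Subject years of exposure will be presented overall and by modal dose for the Safety Analysis Set". Each subject's duration is defined in SAP 3.2.7 as "date of last dose of BRV minus the date of first dose of BRV plus 1 day".

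**After the last dose.** SAP 3.2.4 starts the Post-Treatment Period the day after the last dose, "irrespective of entering the Down-Titration Period, and there is no end date".

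**Size and follow-up.** SAP 2.4 records that "a total of 108 subjects have been enrolled into N01315". Protocol 8.4 leaves the duration open, and SAP 5.1 tabulates retention from 3 to 60 months. Neither document gives mean or total exposure.

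**Background risk.** Protocol 6.1 says: "Sudden unexpected death, a complication of great concern, occurs in 1 to 5 per 1000 patient years". It stands in the epidemiology section, and neither document plans a comparison with it.

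**The concern.** Long-term safety is the primary objective and there is no comparator arm, so a reader can place the deaths only against rates from elsewhere, which are usually given per unit of time. A percentage of subjects does not allow that when one subject may contribute three months and another five years. Protocol 13.4.2 recognises unequal follow-up and asks for results by duration of exposure where applicable, but the death line carries no such breakdown.

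The reader can divide the planned death count by the planned subject-years, but the two need not cover the same time. The numerator has no stated end; the denominator ends at the last dose. When only a handful of deaths is plausible, moving one death across that boundary changes the rate materially. The planned output also gives no interval, so a result of no deaths would print as 0% with nothing to show how little that excludes.

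**Working it through.** The documents contain no mortality calculation to reproduce. The check asks what the planned percentage conveys, what a rate would add, and how large the mismatch can be.

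**Inputs**
- Subjects: 108 enrolled (SAP 2.4), all assumed to be in the Safety Analysis Set.
- Mean exposure: not given. Assumed 1 to 4 years, so T = 108 × 1 = 108 to 108 × 4 = 432 subject-years.
- Background range for sudden unexpected death: 1 to 5 per 1000 patient-years (Protocol 6.1).

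**Formulas**
- Percentage = 100 × d / 108.
- Rate per 1000 = 1000 × d / T.
- Exact Poisson 95% limits per 1000: lower = 1000 × χ²(0.025; 2d) / (2T); upper = 1000 × χ²(0.975; 2d + 2) / (2T). For d = 0 the lower limit is 0.

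**One death and no deaths.** One death is 100 × 1 / 108 = 0.93% in every row.

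| Assumed mean exposure | T | Rate for 1 death (95% CI) | Upper limit for 0 deaths |
|---|---|---|---|
| 1 year | 108 | 9.3 (0.23 to 51.6) | 34.2 |
| 2 years | 216 | 4.6 (0.12 to 25.8) | 17.1 |
| 3 years | 324 | 3.1 (0.08 to 17.2) | 11.4 |
| 4 years | 432 | 2.3 (0.06 to 12.9) | 8.5 |

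The same 0.93% corresponds to a fourfold range of rates. For one death the point estimate passes 5 per 1000 at T = 1 / 0.005 = 200 subject-years, a mean of 200 / 108 = 1.85 years. Every interval in the table contains the whole of 1 to 5 per 1000.

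**Expected sudden unexpected deaths at the background rate.** T × 0.001 to T × 0.005 gives 0.11 to 0.54 at 108 subject-years and 0.43 to 2.16 at 432.

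**Size of the mismatch.** The scheduled drug-free period lasts at most 4 weeks (Protocol 5.2). Serious events are routinely collected for 30 days after each subject's end of study (Protocol 12.2.2). If every subject contributed both in full, the person-time left out of the denominator would be 108 × (28 + 30) / 365.25 = 17.1 subject-years, which is 16% of 108 or 4% of 432. That is small beside the intervals. Misplacing a death matters more: with one death on treatment and one after it, at T = 216, the crude quotient is 2 / 216 = 9.3 per 1000, against 1 / 216 = 4.6 for on-treatment deaths only.

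**The case against.** The strongest reply is that little is lost.

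- **The denominator is planned.** Total subject-years are reported for the same analysis set as the deaths. If the only deaths are on treatment, the quotient is exact for the on-treatment window. This stands: a reader might infer that no rate can be recovered, and that is too strong.
- **The mismatch is bounded and traceable.** About 17 subject-years is a ceiling for the scheduled windows. SAP 11.2.2 tabulates adverse events by study period, and SAP 3.2.2 marks days after the last dose, so later deaths can probably be identified. This largely stands, although events thought to be drug-related are reportable without a time limit, and the reader must assemble the answer from several outputs.
- **There is no mortality benchmark.** A reader might take 1 to 5 per 1000 as one and conclude that the same result could pass or fail it. The documents do not support that. The figure is background, it concerns sudden unexpected death and not death from any cause, and no comparison is planned. Whether a point estimate lies above or inside the range decides nothing when every interval covers the range.
- **Sudden deaths may already be visible.** Serious events are tabulated by preferred term, and the search criteria for events of interest are kept outside the SAP. So it cannot be said that such deaths would go uncounted; it depends on coding. Neither document defines or adjudicates sudden unexpected death.

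What survives is narrower: no rate, no interval and no stated window for the gravest outcome of a long-term safety study.

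**Conclusion.** The point holds as a worthwhile and inexpensive improvement in reporting, not as an error that defeats the study. The percentage alone cannot be interpreted under unequal follow-up: 0.93% may mean 9.3 or 2.3 deaths per 1000 subject-years across the assumed range. The rate obtainable from the planned tables is approximate and comes without an interval. The addition would not show whether mortality is higher or lower than the background figure; with 108 subjects no presentation can. It would show the rate and how uncertain it is, including an upper limit of about 34 or 8.5 per 1000 if nobody dies.

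This rests on all 108 enrolled subjects having been dosed and on a mean exposure of 1 to 4 years, which the documents do not state. The unit problem and the missing window do not depend on either assumption.

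**What to change.** In SAP 11.2.2:

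1. Keep the count and percentage of deaths, and add all-cause deaths per 1000 subject-years with an exact Poisson 95% interval.
2. Pre-specify one at-risk window and apply it to both deaths and person-time. One example runs from first dose to the earlier of last contact (a death counting as last contact) or 30 days after the last dose. Stopping at the date of last dose would be a poor choice: dosing is morning and evening, so a subject who dies overnight after an evening dose would fall on the next day and leave the rate.
3. List deaths after the window separately.
4. Report deaths coded as sudden unexpected death as a separate count by preferred term. Quote the protocol's 1 to 5 per 1000 patient-years only beside that count or its rate, as descriptive context, and not beside the all-cause rate.

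The cost is SAP wording, one more table row and the separate sudden-death count. Person-time needs a small extension of the subject-years already calculated, and no new data or hypothesis test is needed. The drawback is a wide interval, and because sudden unexpected death is not defined or adjudicated, its count will be only as reliable as the coding.
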